### **PREAMBLE**

Research into the factors limiting the public health impact of latent TB infection (LTBI) treatment has focused almost exclusively on adherence to treatment once it has been initiated. However there are many steps prior to treatment initiation – including the initial identification of those at risk, screening them, completing the diagnostic testing and medical evaluation, and acceptance of therapy - by providers and patients. Drop-outs during these steps account for greater reduction of the public health impact of LTBI treatment than failure to complete therapy once it is initiated. Patients who initiate treatment are already "in the system", so they are easy to study. The other patient groups are more difficult to study, so we remain in the dark about who they are, why they drop out, and what to do about them.

On a global scale, in the past 20 years, the predominant focus of LTBI treatment research has been the evaluation of shorter regimens in order to improve treatment completion. As part of that effort, we are conducting a large scale multi-center international randomized trial to compare the efficacy and effectiveness of 4 months Rifampin (4RIF) versus 9 months Isoniazid (9INH) for LTBI. Our trial (which has completed recruitment and treatment of 6840 adults and children, and will complete final follow-up in late 2016) addresses the issue of improving adherence to treatment once it is started, but not all the pre-treatment processes. The current proposal addresses the pre-treatment problems; results from the combination of trials should address all problems – from screening and diagnosis to treatment of LTBI.

We are planning a pragmatic cluster randomized trial to assess a new rapid and standardized approach to improving TB prevention. We have identified sites in Canada, Benin, Brazil, Ghana, Indonesia and Vietnam to conduct this study, with the objective of expanding this approach through-out these countries, if successful. This protocol describes the trial.

### **BACKGROUND - THE NEED FOR A TRIAL**

#### **Importance of tuberculosis globally (why study TB?)**

As a disease, tuberculosis (TB) is unique in that it is wholly preventable and treatable, yet on a global scale, incidence and mortality rose from 1990 until 2005, and the total number of cases is still increasing. The World Health Organization (WHO) has estimated that there are between 8 and 9 million new cases each year, and that 30 million will die from TB over the next decade – close to the total population of Canada!! As well, WHO has estimated that close to **two billion people** have LTBI, of whom approximately 10% – or 200 million persons alive today - will develop active TB during their lifetime. Despite these remarkable facts, many consider this disease to be of little current significance or importance. In many high income countries, after decades of decline, incidence of tuberculosis increased in the 1980's. In most, with greater investment in TB control, rates have since levelled off or declined somewhat.

#### **Importance of TB in Canada (why study TB in Canada?):**

Incidence of active TB in Canada declined steadily from the beginning of the 20th century, although this decline has slowed

since the mid 1980's. In 2012, overall incidence was 4.6 new active cases per 100,000 population, but rates were substantially higher in certain populations and regions, because TB remains a disease of poor and marginalised populations. Incidence among aboriginals ranges from 25 to 100 per 100,000 compared to less than 2 per 100,000 among non-aboriginal Canadian-born. Rates among the foreign-born are three times higher than the national average.

### **Strategies to prevent TB – theory, problems and potential solutions:**

Pathogenesis - Transmission of TB and development of latent TB infection: TB is transmitted by the airborne route from persons with active contagious and untreated pulmonary TB to persons without prior infection. In more than 95 % of healthy persons this new infection does not result in disease, but rather the TB bacilli enter a latent or dormant state; this may last only six months or lifelong. Latent TB infection (LTBI) causes no symptoms, and is not contagious. Usually the only detectable abnormality, and the only means of diagnosis is a positive tuberculin skin test (TST) or an interferon gamma release assay (IGRA). Of persons with LTBI between 5% and 10% will reactivate to active disease over their lifetime. The risk is highest in the first 2 years but other medical illnesses or therapies that suppress the immune system will increase the risk of reactivation at any time. Treatment can be given to those with LTBI which will reduce the risk of reactivation by 60-90% depending on the drug given, and the number of doses taken.

Preventing TB through active case finding: The most fundamental method of TB prevention is to prevent transmission. One approach to reduce transmission is earlier diagnosis of active TB through active case finding, as this will reduce the duration of the contagiousness. Mass x-ray screening was an important method of TB control in many high income countries between 1930 and 1960, but was abandoned as yield diminished. In low and middle income countries there is limited evidence of a role for active case finding. Community-based active case finding had no impact on long term epidemiologic trends in Zambia and South Africa, but was associated with reduced TB prevalence in Zimbabwe.

Preventing TB through Contact investigation: Contact investigation refers to the investigation of persons who have recently been exposed to a person with untreated active contagious TB. Active TB is found in 2-5% of contacts; yield is greater if the source case is more contagious or the contact was closer or longer. In two systematic reviews of yield of contact investigations, the prevalence of active TB detected ranged from 1% to 5%, depending on contagiousness of index cases, and duration and type of contact. Pooled prevalence of LTBI was 51.5% in LMIC, and 28.1% in high income countries. The detection of large numbers of contacts with active TB, or with LTBI at high risk of TB who will benefit from LTBI treatment, are the two reasons why contact investigation is strongly recommended for TB control in high income and low and middle income countries. A single study has demonstrated that routine household contact investigation resulted in long term reduction in TB prevalence in two sub-Saharan African countries.

Preventing TB through BCG Vaccination: The role of BCG vaccination in TB prevention and control remains controversial, primarily because of the vaccine's uncertain efficacy. BCG vaccination of infants has prevented meningitis and miliary forms of TB consistently in trials. However trials of vaccination of adolescents and adults have provided inconsistent results, possibly because of genetic variability in the vaccine itself. BCG vaccine has no impact on long term TB epidemiologic trends.

### Preventing TB through diagnosis and treatment of LTBI – in theory:

LTBI can be diagnosed with immune based tests such as the TST or IGRA's. If treatment is given with one or more anti TB drugs to those with a positive test the risk of active TB is reduced. In a recently completed survey, we found that more than \$25 million is spent annually in Canada for the diagnosis and treatment of approximately 20,000 persons with latent TB infection. One survey of 110 US health departments found that 127,996 persons initiated LTBI therapy between 2000-2002. It has been estimated

that 290,000-433,000 persons are treated annually for LTBI in the US. Other reports indicate that LTBI therapy is a major component of TB control in many other high income countries. In low and middle income countries the World Health Organization has recommended LTBI therapy for close contacts of patients with smear positive pulmonary TB, and HIV infected persons with LTBI.

Preventing TB through diagnosis and treatment of contacts with LTBI – *in reality*: As shown in Figure 1, there are multiple stages involved in contact investigation – termed the Cascade of Care in Latent TB. At each stage of this cascade, there are drop-outs – due to failure to identify individuals who should be screened, screening test positive individuals who did not complete medical evaluation, providers not recommending therapy, or patients refusing to accept or complete recommended therapy. As seen in Table 1, several published evaluations of large scale LTBI treatment programs in the US and Canada have documented dropouts and losses at every stage. Importantly, the problems at each pre-treatment stage resulted in greater cumulative loss of program effectiveness than non-completion of LTBI therapy, once it was started. There are few studies of this cascade of care in LTBI in low and middle income countries. In Thailand and Malawi less than 10% of contacts of active cases were seen for initial screening; in Uganda only 11% of HIV infected persons completed TST screening.

There have been several extensive reviews, and meta-analyses of trials of LTBI treatment regimens., but only one systematic review of adherence to LTBI therapy (once started); completion rates ranged from 20% to 80%. One systematic review of counselling found three trials in which counselling improved LTBI completion. There have been no systematic reviews of the completion of the different stages of the entire LTBI screening process (ie no reviews of the entire Cascade).

## **Background to study methods**

We propose a pragmatic cluster randomized trial, of a public health intervention. These methods have been used successfully in other settings to address many different questions.

### Pragmatic trials:

In many randomized trials, particularly of new therapies, patients are carefully selected to exclude those at risk of non-adherence or adverse events, and then followed very closely to ensure high completion rates, and minimal sequelae of adverse events. These explanatory trials may be justified to assess safety and efficacy of new therapies, but will over-estimate effectiveness and safety. Pragmatic trials are designed to simulate patient selection and follow-up conditions of usual practice to provide realistic estimates of the intervention's effect and safety. Hence in a pragmatic trial, patients at risk of non-completion, and/or adverse events are included. The ongoing 4RIF versus 9INH trials in adults and children are pragmatic trials, in that patients who are candidates for LTBI therapy are excluded only if they have absolute contra-indications to 4RIF or 9INH, and the follow-up of trial participants during treatment simulates usual practice as much as possible. (For safety and determination of end points, follow up and investigation is much more intensive, if patients are suspected to have adverse events or active TB).

### Cluster randomization:

When the study intervention must be given at a group level then the unit of randomization must be at a group level. Examples of group-level interventions include fluoridation of a town water supply, public education campaigns, or implementation of new diagnostic or treatment methods at a health facility. With this study design, outcomes may be measured at the level of the individual, but because of the correlation of outcomes among individuals in the same group, statistical power will be reduced, sample size must be increased accordingly, and the statistical approach must account for this correlation.

Table 2 provides a few examples of recent cluster randomized trials.

## **Summary of current evidence:**

Investigation of contacts of newly diagnosed active pulmonary TB is important for TB control in all countries, as has recently been emphasized by WHO. This detects active TB, as well as persons with LTBI who are at high risk of active disease. The numbers of contacts investigated in the US and Canada is not known, although more than 20,000 persons in Canada, and 300,000 persons in the US initiate LTBI therapy each year, mostly with 9INH, which is considered the standard of care, but has very poor completion rates. These poor completion rates have spurred substantial investigation into solutions – particularly shorter regimens. However, a largely ignored problem, demonstrated in several studies of large-scale LTBI diagnosis and treatment programmes, is that even before patients initiate LTBI therapy, far greater numbers have already dropped out or been lost during the pre-treatment phase of these programmes. These pre-treatment problems cause greater reduction of the public health impact of LTBI treatment, than non-completion of treatment. However, there have been very few studies exploring the reasons for these pre-treatment losses, and no intervention studies.

### **Prior relevant work by the investigators:**

In the past 20 years, the major focus of efforts to improve LTBI treatment completion has been the development and testing of shorter LTBI regimens. As a result, there are now three alternatives to INH. The combination of 3 or 4 months of INH and Rifampin (3INH-RIF) has similar efficacy, completion and toxicity as 6 months of INH (6INH). A regimen of 12 doses of INH and Rifapentine (a long acting Rifamycin) given once a week and directly observed had superior completion, similar toxicity and equivalent efficacy to 9INH. Another recommended alternative is 4 months of Rifampin (4RIF). In mouse studies 2RIF, and among older Chinese men with silicosis and LTBI, 3RIF were as effective as 6INH.

### **Randomized trials of shorter regimens for LTBI:**

Since 2001 we have embarked on a series of randomized trials to compare 4RIF to 9INH. The first trial demonstrated significantly superior completion and somewhat fewer adverse events with 4RIF. In the second trial completion was significantly superior, costs were significantly lower, and serious adverse events, particular grade 3-4 hepatotoxicity, significantly less with 4RIF. We are currently nearing completion of two large-scale international multi-center randomized trials – to compare safety, efficacy and effectiveness in 6040 adults, and safety and tolerability in 824 children, of 4RIF or 9INH (see Appendix 6: Results from 4RIF v 9INH Phase 1, 2 and 3 trials). The pediatric trial completed enrolment in October 2014, and all follow-up will be completed in January 2016. Enrolment in the adult trial was completed in December 2014, the last patients are finishing treatment in September 2015, and will complete post-treatment follow-up in early 2017. The proposed trial will be conducted at many of the same sites – enhancing feasibility and cost-effectiveness, and facilitating expansion of LTBI treatment there.

### **Pilot study in Brazil:**

In 2014 funding was awarded by the Brazilian government for the conduct of a pilot study in 3 cities – Rio de Janeiro, Manaus, and Recife - in Brazil (PI [name]). This experience will allow us to make extensive revisions to all study tools to be used in other sites during the main study and cross over. Specific objectives of the pilot study are:

1. To assess feasibility of the public health intervention itself – ie Phase 1 evaluation, then transition, and Phase 2 - implementation of solution.
2. To assess the utility of the questionnaires, cascade analysis, time and motion study as well as health facility questionnaires i.e. all instruments used in Phase 1.
3. To assess the cross-over design, with shortened phase 1 and Transition.
4. Further revise the questionnaires – which will later be used by all other sites in their cross-over phase.

**Pilot study Site:** In Brazil, since 2010 the NTP has recommended that all (regardless of age) close contacts of newly diagnosed pulmonary TB cases are investigated and treated for LTBI free of charge. Community health agents visit contacts at home, and refer them to a nearby clinic for TST. Those with a positive TST have a CXR. Physicians prescribe self-administered LTBI treatment. Contact investigation and LTBI management are recorded and should be reported to the NTP. Brazil has traditional polyclinics with physicians and nurses, and diagnostic facilities, and Family Health Team clinics. The adult and pediatric 4RIF vs 9INH trial is being conducted at 3 polyclinics, and one Family Health Clinic in Rio de Janeiro. The pilot study will be conducted in Brazil alone with 4 health facilities in Rio de Janeiro which will be intervention and control sites and an additional 2 health facilities in Recife and 2 health facilities in Manaus.

### **How will the results of the trial be used?**

LTBI diagnosis and treatment is a key element of TB control through-out the world, and is now being promoted by WHO , particularly in high risk groups such as HIV infected and close contacts. However, there are substantial limitations to this approach – particularly in low and middle income countries. We are nearing completion of two large scale trials of LTBI therapy in Canada and six LMIC, as summarized above. These trials have demonstrated that LTBI diagnosis and therapy is well accepted, feasible and safe in all settings. But experience to date is limited to a few centres within the LMIC, where there are well trained and experienced staff. To scale up LTBI diagnosis and treatment in these countries is a major challenge as there are many barriers. This trial will be the first to systematically introduce and evaluate affordable, simple and feasible interventions to address these problems.

The proposed study will test a complex intervention – a programmatic public health package. This package will consist of standardized public health evaluations to identify problems limiting LTBI diagnosis and treatment among close contacts of active TB cases. This will be based on a framework for analysis and resolution of the problems, based upon the Cascade of Care in Latent TB framework. We will develop procedures for analysis and evidence-based decision making to select solutions to resolve the problems identified. This will include a system of initial training, followed by on-site in-service training during regular visits to consolidate the new interventions. This combination of evaluations linked directly to action should be readily applicable by public health practitioners. We will limit the resources used for these solutions to be equivalent to the costs, in the same setting, of treating patients with active TB. This should ensure the interventions evaluated are affordable and cost-effective (if not cost saving) in the settings where they are needed.

We will develop and use standardized tools – teaching aids for providers, patients with active TB, and with LTBI, as well registries and other methods for recording and reporting. These tools will facilitate subsequent programmatic scale up of enhanced LTBI diagnosis and treatment in low and middle income countries. The findings from Canada should be applicable to other high income countries. Trial results will be disseminated within each country readily as the investigators in all countries have close links to the leadership of their national TB programmes. The Contact Management Registries and reporting procedures are designed for easy uptake by NTP programmes and staff, and will be given to these programme leaders, plus posted on Websites. In addition several of the investigators have worked extensively with WHO, PAHO (Pan-American Health Organization), the International Union Against TB and Lung Disease, Health Canada, Centres for Disease Control (US) and USAID – and have a strong track record of knowledge translation with these organizations. These contacts will be used to enhance dissemination (eg endorsement and publication of these tools by WHO).

## **THE PROPOSED TRIAL – HYPOTHESIS, OBJECTIVES AND DESIGN**

### **Study Hypothesis:**

An intervention package of a standardized public health evaluation and needs assessment, followed by targeted solutions for problems identified will enhance the proportion of household contacts of patients with newly diagnosed active pulmonary TB who initiate treatment for LTBI.

### **Study Objectives:**

**Primary:** To evaluate the effectiveness of a standardized public health evaluation followed by targeted solutions for problems identified to increase the proportion starting LTBI treatment among household contacts of patients with active pulmonary TB, during the last 6 months, of an 18 month cluster randomized trial;

### **Secondary:**

- 1) To evaluate the effectiveness of the standardized public health evaluation and solution packages at improving: the proportion completing LTBI treatment, of those who start.
- 2) To evaluate the health system costs associated with current management of active TB, contact investigation, and latent TB diagnosis and treatment as well as the costs associated with the evaluation and implementation of appropriate solutions – including staff time and other resources used – in order to assess their feasibility, and cost-effectiveness.
- 3) To evaluate the sustained effect of this complex intervention for one year after the end of the randomized trial
- 4) To evaluate the costs, and impact of a stream-lined Phase 1 and 2 – administered to control sites, after the 18 month trial.

### **Study design:**

We propose a cluster randomized trial at 36 sites in 6 countries. Sites randomized to the intervention group will receive a complex two-phase intervention lasting 18 months. Control sites will receive a stream-lined version of this 2-phase intervention after 18 months, while outcomes are continued to be measured at all sites for an added 12 months.

**Randomization** will be stratified by country, and restricted to ensure equal number of participants receiving or not receiving the intervention within each country. Following randomization, **in Phase 1**, a standardized public health evaluation will be conducted at all intervention sites to identify barriers to LTBI diagnosis and treatment initiation, in order to select the solutions to be used in Phase 2. This will include measurement of the key study outcomes (see below). To ensure standardization of data gathering we will use (i) current indicators of the LTBI cascade of care in the participating units (number of contacts per index case registered, investigated, started on treatment and completing treatment) and (ii) interviewer-administered standardized questionnaires – for patients with newly diagnosed active pulmonary TB, household contacts of these patients, clinic staff and administrators. These questionnaires will assess management of contacts, LTBI diagnosis and therapy, as well as TB-related knowledge, attitudes and beliefs from the perspective of these different participants. Results from this phase will be analysed, and used by the investigators, together with local public health officials, to decide on appropriate corrective solutions. In control sites we will gather data on study outcomes only (see below).

**In Phase 2**, solutions will be selected, and implemented at the intervention sites. Preparations and training of staff at each site will be conducted before the intervention begins, as soon as each site (clinic) is judged ready to begin. Study outcomes will continue to be measured at all sites through-out Phase 2.

### **Rationale for study design**

The study is designed as a pragmatic public health intervention study in that the intervention package will be tailored to the problems identified from the standardized public health evaluation in that country.

The specific problems and changes required will not be exactly the same in all sites, raising potential concerns over generalizability. **However the intervention being tested is the approach – a standardized public health evaluation and analysis, with identification of problems (barriers), and appropriate solutions.** The initial evaluation will utilize standardized questionnaires, and data gathering to facilitate replication in other settings. We have reduced the variability of the final solutions package by limiting the budget allocated for these solutions. This type of public health intervention has been used successfully in other cluster randomized trials - training hospital staff in Senegal and Mali to conduct maternal mortality review resulted in reduced maternal mortality, and facilitation of women's group meetings in Nepal lead to improved birth outcomes. In both studies the actual solutions that were implemented were site-specific; it was the process to identify problems that was standardized.

The choice of LTBI treatment regimen by the primary providers will follow local treatment guidelines. This for several reasons: i) The primary objective of the trial is to evaluate interventions up to treatment initiation – which will not be affected by the treatment selected; ii) The current standard in most countries remains INH for 6 or 9 months; iii) The 4RIF vs 9INH trial will only be finished in early 2017, so findings from that RCT will not affect practise until close to the end of this study.

We are not planning solutions aimed at enhancing treatment completion (once it has been initiated). Patients will be followed in the usual fashion by their usual providers, until treatment completion. This reflects our belief that the problems encountered in the different pre-treatment evaluation steps have not been adequately studied; hence very few effective interventions have been identified. However, it is evident that LTBI treatment completion is necessary in order for LTBI investigation and treatment to achieve long term individual and public health benefits. Therefore treatment completion will be documented, and analyzed. If treatment completion is less than 50%, this will be a focus of in-service training and other solutions.

In this study blinding of patients with active TB, their contacts, and the health workers to the public health interventions will not be possible. This is similar to many other cluster randomized trials, including many published large scale trials in TB. Given this, the outcomes, and their ascertainment must be as objective as possible. Outcomes will be ascertained from written Contact Registries, and are objective (persons either are identified, complete testing, come to health facilities, etc, or they do not).

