### **Ascertainment of study outcomes - at all sites:**

Ultimately, in the intervention sites we will be able to use the newly developed and introduced Contact Management Registries (see below) to extract all necessary information and outcomes – including number of pulmonary TB cases (Index cases), number of contacts identified, and number who initiate LTBI therapy. However, these detailed contact registries are considered an integral part of the public health intervention, since considerable training in recording and reporting as well as the procedures of contact management will be needed for these to be completed accurately and completely. Introduction of these registries at control sites would be difficult without extensive training; if such training was given at the control sites, this would constitute a partial intervention, and reduce potential differences between intervention and control sites.

Hence recording of outcomes at control and intervention sites must rely on simple measures that can be implemented with minimal training, prior to the start of the trial at all sites. It is important that the procedures to ascertain (measure) these outcomes be established at the beginning of Phase 1, and continue **unchanged** at all health facilities (both intervention and control facilities) through-out the 18 months of the study.

Identification of contacts may not be performed, or not clearly recorded at all health facilities – especially the control facilities. This is why we must carefully document the number of index patients with active pulmonary TB diagnosed at each site. When the study is completed, the coordinating centre may use the number of index cases to estimate the number of household contacts that likely could have been identified (see Analysis section) Data sources will vary by site, depending what methods of documentation are already being used. We will collect information on the number of newly diagnosed index cases from lab or other sources that report active cases. The number of household contacts indentified will come from different sources depending on what is available the site. Finally, we will estimate the number of contacts who start LTBI treatment from hospital and or clinic records using a standard data collection form in all sites. The number of contacts completing LTBI therapy will be estimated retrospectively from clinic records.

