**Reporting:**

The Contact Management registries will be used to generate quarterly reports of diagnoses of contacts, and cohort reports of treatment outcomes in TST positive contacts. These quarterly reports will be modeled after the quarterly reports of case finding, and treatment outcomes that are recommended by WHO , and used by the National TB control programmes in almost all LMIC.

The quarterly reports will be based on data abstracted from the Registries (they are designed to be abstracted very easily), and initially prepared by study staff. These reports will include the number of new pulmonary TB patients, household contacts identified, investigated with symptom screening and TST, had TST reading, TST positive who underwent medical evaluation, and initiated LTBI medication.

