### **TIME-TABLE OF PHASE 2:**

The chronology can be summarized as:

Months 6-8: Selection/confirmation of solutions, and methods for contact identification, diagnosis, treatment and reporting. Training, then introduction of solutions at the sites (as soon as each site is prepared). Continued outcome measurement at all sites.

Months 9-12: All intervention sites have started, and are 'scaling up' to fully implement all planned solutions.

Months 13-18: Full implementation of all solutions at all Intervention sites

Data analysis – we anticipate this will be finished quickly as it is very simple – involving simple counts of outcomes from the contact diagnosis and Contact treatment quarterly reports, with verification from the source documents – the Contact Registries

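### Two protocol sentences take the outcomes from the new Contact Registries, which control clinics will not have during the trial, and so contradict the protocol's own rule of one simple, unchanged method at all sites

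*Protocol*

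**What the plan says.** The Protocol gives two accounts of where the outcome data come from.

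**Account A: the registries.**
- Rationale for study design: after conceding that blinding is impossible, the protocol offers objective ascertainment as the safeguard and states "Outcomes will be ascertained from written Contact Registries, and are objective". The sentence is not limited to one arm.
- Time-table of Phase 2: the data analysis is described as "simple counts of outcomes from the contact diagnosis and Contact treatment quarterly reports, with verification from the source documents", and the source documents are named as the Contact Registries.
- Phase 2 Enhanced Reporting, Reporting: "The quarterly reports will be based on data abstracted from the Registries". Counting from the quarterly reports is therefore counting from the registries.

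**Account B: simple common measures.**
- Ascertainment of study outcomes - at all sites: "these detailed contact registries are considered an integral part of the public health intervention". It adds: "Introduction of these registries at control sites would be difficult without extensive training", and says such training would amount to a partial intervention.
- The same section concludes: "Hence recording of outcomes at control and intervention sites must rely on simple measures that can be implemented with minimal training". The procedures are fixed at the start of Phase 1 and are to stay unchanged "at all health facilities (both intervention and control facilities) through-out the 18 months of the study".
- Study Outcomes: index cases, identified household contacts and treatment starts are measured monthly at every facility in both arms, on a standardized form.
- Contact Management Registries: registry treatment starts are compared with the other methods of ascertaining the primary outcome in the final 6 months, as a secondary analysis.
- Secondary study, Phase 2: use of the new registries at all sites is placed in the cross-over, after the 18-month trial.

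**The concern.** Both accounts are current text and they cannot both hold. Account A cannot be carried out at control clinics during the randomized period, because the new registries are not there. Someone who follows the timetable sentence would have to use the registry in the intervention arm and something else in the control arm.

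The primary outcome is the proportion of identified contacts who start LTBI therapy in the final 6 months. By then intervention staff have been trained on the registry, and research staff have reviewed it at repeated in-service visits. Control clinics would be measured from routine records, and the protocol itself warns that identification of contacts may be poorly recorded there. Any difference in completeness of recording would enter the estimated risk difference. Neither the GEE model nor multiple imputation, as described, would remove it, since a start or contact that was never recorded does not appear as a missing value.

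The sentence in the rationale matters for a second reason. It is the stated defence of an unblinded trial, and it rests on a source that one arm lacks.

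**Working it through.** **Consistency check.** No figure in the protocol is at issue, so the main check sets the passages side by side.

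| Question | Rationale; Phase 2 timetable | Ascertainment; Study Outcomes; Registries |
|---|---|---|
| Source of outcome counts | Contact Registries; quarterly reports built from them | Simple measures on a standardized monthly form |
| Available at control clinics in the 18 months? | No | Yes |
| Role of registry treatment starts | Outcome source and verification | Secondary comparison only |

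The two columns are incompatible on every row.

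**What different methods could do.** The protocol gives no completeness rates, so those below are assumptions. Let p be the true proportion starting treatment, the same in both arms (no effect). Let the registry record everything. Let control records capture a fraction c of starts and a fraction f of identified contacts.

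Recorded control proportion = p × c / f
Spurious risk difference = p − p × c / f

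Inputs for scale, from Sample size considerations, Table 2: 100 contacts per clinic and ICC 0.05 give a design effect of 1 + 99 × 0.05 = 5.95 (printed as 6.0). With about 1200 contacts per arm, the effective size is 1200 / 5.95 ≈ 202 per arm. The last column is the normal-approximation probability of a significant result in favour of the intervention at two-sided 0.05. Its value with no bias is 2.5%.

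Control records miss starts only (f = 1):

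| p | c | Recorded, control vs intervention | Spurious difference (points) | Probability |
|---|---|---|---|---|
| 10% | 0.9 | 9% vs 10% | +1 | about 5% |
| 10% | 0.8 | 8% vs 10% | +2 | about 10% |
| 10% | 0.7 | 7% vs 10% | +3 | about 19% |
| 30% | 0.9 | 27% vs 30% | +3 | about 10% |
| 30% | 0.8 | 24% vs 30% | +6 | about 27% |
| 30% | 0.7 | 21% vs 30% | +9 | about 55% |

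Control records miss identified contacts only (c = 1):

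- p = 10%, f = 0.7: 0.10 / 0.7 = 14.3%, a difference of −4.3 points.
- p = 30%, f = 0.7: 0.30 / 0.7 = 42.9%, a difference of −12.9 points.

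If starts and contacts are missed to the same degree (c = f), the two errors cancel. For comparison at the same control rates and ICC 0.05, Table 2 gives detectable differences of 10 points at 10% and 13 points at 30%.

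**The case against.** The strongest reply is that the protocol has already dealt with this. The ascertainment section is the one written to govern the matter. It raises this very problem, rejects registry-based measurement for the trial, and puts the word unchanged in bold. Against it stand one sentence in a rationale and one remark about how quickly the analysis will finish. The Phase 2 analysis section does not name the registries as a source. A careful reader would probably follow the ascertainment section. That is a fair account of the likely intention, and it is why the remedy is small. But nothing in the two sentences defers to that section, and one of them describes how the analysis will be done.

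Four stronger readings are tempting and are not supported:

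- *The ascertainment section contradicts itself, because it opens by saying intervention sites will be able to use the registries for all outcomes.* It does not. The opening is followed by the reason this cannot serve the trial and then by the common rule.
- *The protocol requires identical sources in both arms.* It does not. It allows data sources to vary by site, within simple measures, a standard form for treatment starts and no change over time. It also notes that a few programmes may already keep contact registries. The contradiction concerns the new registries.
- *Better recording would necessarily flatter the intervention.* The outcome is a proportion, and the denominator is recorded by the same systems. Missed contacts raise the control rate and pull the other way.
- *Any spurious difference can be judged against a 10-point detectable difference.* That figure belongs to a 10% control rate at ICC 0.05; other rates need their own comparison.

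The protocol also allows the coordinating centre to estimate the number of contacts from index cases. This could ease the denominator problem, but it is optional and does nothing for missed starts.

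**Conclusion.** The protocol is wrong as written in two places: the outcome-source sentence in the Rationale and the data-analysis paragraph of the Phase 2 timetable. Both contradict the sections on study outcomes, ascertainment and registries. This is more than a clerical slip, because following the timetable text would give differential ascertainment of the primary outcome in an unblinded trial.

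The contradiction itself rests on no assumption. The size of the consequence does. Over the assumed range the spurious difference runs from about −13 to +9 points at 30% starting, and from about −4 to +3 points at 10%. These figures assume complete registries, no true effect, and control records missing up to 30% of either starts or contacts. They show that the bias could be material and could run either way; they do not predict it. The design decision in the ascertainment section is sound and is not in question.

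**What to change.** Amend two places.

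1. **Rationale for study design.** Replace the registry sentence with a statement that primary-outcome counts (index cases, identified household contacts, treatment starts) come, in both arms, from the standardized monthly form and the site's pre-existing records, as set out under Study Outcomes and Ascertainment. Rest the claim of objectivity on that.
2. **Time-table of Phase 2, data analysis.** Say that the analysis counts outcomes from the same monthly form in both arms, and that any verification against source documents is done in the same way in both arms. Add that registry data do not replace or correct these counts and serve only the secondary comparison already described under Contact Management Registries.

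The ascertainment section needs no change. The cost is wording: the monthly form is already planned at every facility, and no new data collection follows unless source verification is carried out, in which case control clinics must be included on the same terms.
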